AV optimisation delivered with direct His bundle pacing, in patients with heart failure, long PR without left bundle branch block: randomised multi-centre clinical outcome study. The His Optimised Pacing Evaluated for Heart Failure Trial (HOPE-HF)

OBJECTIVE

To evaluate whether, a group of heart failure patients who are not currently targeted for pacing therapy for heart failure, will obtain benefit from pacing therapy delivered to allow optimisation of LV preload by shortening Atrioventricular delay.

DESIGN

This is a multi-centre, prospective randomised double-blinded cross over study, recruiting a sub-population of patients with heart failure.

All patients will be implanted with a CRT device with one of the leads positioned on the His bundle in order to obtain direct His-bundle capture. There will be a 2-month run-in period where the device will be programmed not to deliver His pacing therapy during this period.

A double-blinded cross-over design will then be employed to investigate the effect of His pacing. Patients will be allocated in random order to six month treatment periods in each of the following two states (1) No His pacing; (2) AV optimised His-bundle pacing. Endpoint measurements will be taken at baseline, 6 months and 12 months post randomisation. Treatment allocation will be blinded to the endpoint assessor.

SAMPLE SIZE

126 patients will be needed to detect the expected effect size on the primary endpoint with 90% power. A total of 160 patients will be randomised to allow for patient drop-out.

INCLUSION CRITERIA

- Aged 18 or above
- Ventricular Ejection Fraction (EF) ≤ 40%; BNP needs to be ≥250ng/L for patients with EF 36-40%
- New York Heart Association (NYHA) class II-IV
- PR interval ≥200ms
- Narrow QRS duration (≤140ms) or prolonged QRS duration with typical Right Bundle Branch Block (RBBB) morphology on 12 lead ECG and sinus rhythm

EXCLUSION CRITERIA

- Permanent or persistent atrial fibrillation (AF)
- Paroxysmal atrial fibrillation with history of sustained AF (more than 24 hours) in the 6 months prior to screening
- Patients who are unable to perform cardiopulmonary exercise testing
- Other serious medical condition with life expectancy of less than 1 year
- Lack of capacity to consent
- Pregnancy
- Contraindication to use of the relevant study device or leads (as per current manuals from manufacturer)

TREATMENT/MAIN STUDY PROCEDURES

Implantation of pacemaker or Implantable cardioverter defibrillator. In all patients leads will be positioned in the right atrium and at the His bundle. Participants who are not eligible for ICD implantation will have a lead positioned in a lateral ventricular branch of the coronary sinus. Those receiving an ICD will have an ICD lead positioned in the RV apex or RV septum.

AV delay optimisation will be performed using continuous non-invasive blood pressure measurements, with an algorithm to minimise the effect of noise.

PRIMARY ENDPOINT

The primary outcome measure will be exercise capacity, measured using peak oxygen uptake (VO₂).

SECONDARY ENDPOINTS

Secondary outcome measures will be echocardiographic measurement of left ventricular dimensions, quality of life scores, daily activity levels as recorded by the implanted device, cost effectiveness, changes in B-type Natriuretic Peptide (BNP), arrhythmia burden, pacing parameters (e.g. pacing thresholds, R Wave amplitude and lead impedance) and fluoroscopy time at time of device insertion.

1 INTRODUCTION

Heart failure is a major clinical problem, causing a high symptom burden and high mortality rates^{1,2}. In the UK heart failure accounts for 1 million days of inpatient stay per year, this is $\sim 2\%$ of all NHS hospital inpatient days and 5% of emergency admissions³.

Hospitalisation for heart failure is expected to rise by 50% over the next 25 years. Heart failure also causes significant mortality (35% mortality in the first year after diagnosis and then 10% thereafter). There are currently ~900 000 patients in the UK with heart failure³.

Cardiac resynchronisation therapy (CRT) is an important treatment, which has been shown to improve symptoms, reduce hospital admissions^{4,5} and decrease mortality⁶.

However, CRT is only applicable to some patients with heart failure: those who have left bundle branch block⁷. Therefore a new method of pacing therapy that can benefit a group of heart failure patients not currently targeted for CRT would be a major advance.

Currently patients with narrow QRS duration or right bundle branch block are not routinely selected for treatment with CRT because, when tested in a bias-resistant manner, the results have not been favourable^{8,9}. However, these studies did not specifically target the group who are most likely to derive benefit, namely those with a long PR interval. In addition classical CRT when applied to patients with good intraventricular conduction appears to induce a degree of iatrogenic intraventricular dyssynchrony, which may partly offset the benefits of PR interval shortening¹⁰.

PR prolongation in heart failure is associated with poor outcomes (58% higher mortality) regardless of QRS duration¹¹. Shortening a prolonged PR interval with pacing therapy appears to have beneficial effects. In CRT studies performed in patients with LBBB, longer baseline PR interval predicted greater benefit¹². In COMPANION, patients with a long PR interval had a 17% greater risk reduction compared to those with a normal PR interval¹³, an effect size on par with that of mandatory drugs in heart failure¹⁴. Similarly in the MADIT-CRT trial, participants with non-LBBB QRS broadening derived a prognostic benefit from CRT only when the PR interval was above 230 ms, whereas the opposite effect was found when the PR was shorter than 230 ms¹⁵.

In our institution, patients with PR prolongation account for 30% of the non-left bundle branch block heart failure population. Therefore in the UK alone this group of patients is likely to represent ~180,000 patients.

1.1 Rationale for the study

Optimising left ventricular filling by shortening AV delay has been demonstrated to have a powerful effect on acute cardiac function, which is reflected by changes in LV dp/dtmax, stroke volume, coronary artery flow and systolic blood pressure^{16,17,18}. We have developed a haemodynamic method for identifying optimal AV delay settings with pacing therapy for heart failure. The advantage of using systolic pressure is that this is an extra cardiac measure, which reflects the net change in cardiac function occurring as a result of adjustments in intra cardiac timing. In patients with heart failure, contrary to the general population, higher blood pressure is associated with lower mortality¹⁹. The increased blood pressure occurring with more optimal AV delays is reflected by a sustained increase in stroke volume²⁰.

We have previously shown that when haemodynamic measurements are used for AV delay optimisation it is essential to use a method that minimises the effect of noise. Noise occurs with all haemodynamic measurements, regardless of whether they are made

Confidential

invasively or non-invasively²¹. The protocol we have developed for performing AV delay optimisation utilises several steps to ensure precise and reproducible measures are obtained. These include comparing each tested delay to a reference setting and using the mean value of multiple alternations to and from the reference setting²². We have shown that it is most efficient to sample immediately after a transition²¹, to use a sampling window which includes the number of beats occurring in 1 respiratory cycle and to perform measurements at an elevated heart rate²³. We have shown that this method is highly reproducible when used for AV delay optimisation^{22,17}.

As discussed above, improving LV preload by shortening AV delay appears to be an important mechanism through which CRT delivers its beneficial effect in patients with left bundle branch block and heart failure¹³. Patients with narrow QRS duration and PR prolongation may also be expected to obtain benefit from AV delay optimisation. However, applying CRT pacing to patients with good intraventricular conduction appears to induce a degree of iatrogenic intraventricular dyssynchrony which has the potential to partly offset the benefits of PR interval shortening¹⁰.

In patients with an intact intraventricular conduction system, a special form of pacing called direct His-bundle pacing, offers the potential to stimulate ventricular contraction while preserving ventricular activation patterns^{24,25,26}. Permanent direct His pacing has been shown to be feasible when it has been applied in patients who have a bradycardia indication for pacing²⁷ or to reverse proximal LBBB in patients who have failed a conventional LV lead implant²⁸.

Permanent direct His pacing has never been assessed as a method for delivering AV delay optimisation to patients with narrow QRS duration or RBBB and heart failure. We have assessed the acute haemodynamic effect in this patient population and found favourable results²⁹.

Therefore in this study we will evaluate whether, a new group of heart failure patients who are not currently targeted for pacing therapy for heart failure, obtain benefit from pacing therapy delivered to allow optimisation of LV preload by shortening AV delay.

Our study involves two novel aspects. Firstly, in order to reduce the risk of causing harm by inducing ventricular electrical dyssychrony, we will use a special form of pacing – direct

His bundle pacing- which has not previously evaluated in this context. Secondly, we will use a novel method for identifying optimal AV delay, which is designed to ensure precise and reproducible values are obtained.

1.2 Intervention details

All patients will be implanted with a Pacemaker or Implantable cardioverter defibrillator (ICD).

All participants will have pacemaker leads positioned in the right atrium (typically the right atrial appendage) and on the His bundle in order to obtain His-bundle capture. If it is not possible to successfully implant a His-bundle lead with selective direct His bundle capture or non-selective capture with < 40ms prolongation of the QRS duration, then a lead will be implanted in a lateral branch of the coronary sinus as an alternative approach.

In patients who do not have an indication for an Implantable cardioverter defibrillator (ICD) a second ventricular lead will be implanted in a lateral branch of the coronary sinus. If His pacing has not been successfully achieved then a further lead will be positioned at the RV apex. In patients who have an indication for an Implantable cardioverter defibrillator the ICD lead will be positioned in the right ventricle (either RV apex or RV septum).

Confidential

Implantation procedure:

Implanters will undergo training in His bundle pacing and will be provided with detailed guidance regarding the device implantation protocol. In brief the implant process will include the following steps.

Venous access will be obtained in the standard way and an atrial lead will be implanted in the right atrial appendage. In patients receiving Implantable cardioverter defibrillator the ICD lead will next be implanted in the conventional way targeting the RV apex or RV septum.

His bundle pacing: a Medtronic Select Secure 3830 pacing lead will be positioned at the His bundle using a 9 French delivery sheath (either the Medtronic C315 fixed shaped catheters or the Medtronic SelectSite C304 deflectable catheter). His capture will be confirmed using the criteria previously described by Deshmukh et al¹⁸. In brief these consist of confirming the following: a) 12 lead ECG morphology match with direct His bundle pacing compared with intrinsic conduction, b) similar time delay between the stimulation artefact and the onset of the QRS complex compared with the intrinsic His to QRS time, c) His bundle capture in an all or none-fashion, demonstrated by the absence of QRS widening at a lower pacing output.

If selective His bundle pacing cannot be achieved then non-selective His bundle pacing will be accepted. Non-selective His pacing is defined as the direct capture of the basal ventricular myocardium in addition to His bundle capture.

Patients will be randomised to 6 months of the following:

1) *Active treatment*: His bundle pacing with the AV delay programmed to the optimal sensed and paced delays identified during the optimisation process

2) *No His pacing treatment:* pacemaker programmed to avoid pacing as per the implanting physicians discretion utilising the non His ventricular lead (suggested modes are VVI 30, DDD/I 30 etc). His pacing should only be programmed on active treatment.

Dynamic AV delay will be programmed off throughout the study.

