2.4 Secondary Endpoints

Secondary outcome measures are:

- (1) Echocardiographic measurement of left ventricular function and remodelling
- (2) Changes in B-type Naturietic Peptide (BNP)
- (3) Changes in Quality of Life Scores
- (4) Changes in daily activity levels recorded using objective metrics from the pacemaker device
- (5) Cost effectiveness analysis
- (6) Percentage pacing will be recorded, as will arrhythmia burden (atrial fibrillation, atrial flutter and ventricular arrhythmias), pacing thresholds, R wave amplitude and lead impedance. Fluoroscopy time during device insertion will also be reported.

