5.4 Randomisation and Crossover

Two months after patients are implanted with their device, patients will be randomised to either receive active His pacing treatment or no His pacing treatment (e.g. pacemaker programmed to VVI or DDD/I 30 bpm). After a further 6 months, they will be crossed over to the alternative treatment arm. Treatment allocation will be obtained using an Interactive Web Response System (IWRS) programmed with a randomisation schedule provided by the trial statistician. Appropriate blocking will be used.

The patient will have study assessments listed in table 1 and described in the section 5.5.

The physiologists performing study tests will be blinded to the treatment arm. A separate investigator will be responsible for programming the device.

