6.4 Monitoring Device Performance

Device data will be reviewed in person when patients attend for review at Visit 3, 4 and 5 (2 months, 8 months and 14 months post device implantation respectively). This will provide details on pacing thresholds, R wave amplitude and lead impedance. Details of any arrhythmia will also be seen. This data will be included in reports to the DMC for monitoring of any adverse consequences.

Device follow-up after cessation of the trial will be at the patient's local cardiology centre.

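### Atrial arrhythmia burden is a secondary outcome, but the protocol does not require atrial recording to be the same with His pacing on and off; if VVI control reduces it, His pacing would falsely appear to raise AF

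*Protocol*

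**What the plan says.** **The endpoint.** Protocol section 2.4, item (6), includes "arrhythmia burden (atrial fibrillation, atrial flutter and ventricular arrhythmias" among the secondary outcome measures. The secondary endpoints in the trial summary agree, listing "arrhythmia burden, pacing parameters (e.g. pacing thresholds, R Wave amplitude and lead impedance".

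**The source.** Section 2.4 does not say how arrhythmia burden is measured. Section 6.4 describes device interrogation at visits 3, 4 and 5 and adds: "Details of any arrhythmia will also be seen". It then says "This data will be included in reports to the DMC for monitoring of any adverse consequences".

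**Active state.** Section 1.2 defines it as "His bundle pacing with the AV delay programmed to the optimal sensed and paced delays" found at optimisation.

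**Control state.** Section 1.2 has the "pacemaker programmed to avoid pacing as per the implanting physicians discretion", and gives examples: "suggested modes are VVI 30, DDD/I 30 etc". Section 5.4 repeats the choice: "no His pacing treatment (e.g. pacemaker programmed to VVI or DDD/I 30 bpm".

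**The analysis.** Section 8.2(i) applies the crossover model for the primary outcome to differences in secondary outcomes as well.

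**The concern.** A within-patient comparison of AF burden is fair only if AF is equally likely to be recorded in both six-month periods. Active treatment uses a sensed AV delay, so the atrium must be sensed. In control, sensing depends on which mode the programmer picks, and one of the named modes senses only the ventricle by its code.

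Any loss of atrial recording that follows from this would fall on control periods alone. Randomising the order and crossing over would not cancel it, because it follows the treatment state and not the period or the patient. The error would run one way, towards more apparent AF on His pacing. That matters because AF burden has a safety meaning and the DMC receives the device data. It also cannot be repaired in the analysis: AF that was never recorded cannot be recovered.

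**Working it through.** **Step 1: is the difference in recording possible under the text?**

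| Question | Active | Control |
|---|---|---|
| Atrial sensing implied? | Yes, by the sensed AV delay (1.2) | Depends on mode: DDD and DDI sense the atrium, VVI does not (1.2, 5.4) |
| Who fixes the mode? | Protocol | Implanting physician (1.2) |
| Is atrial arrhythmia recording required? | Not stated | Not stated |

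**Step 2: is there another record that could measure burden?** Appendix 2 schedules ECGs only at screening and implantation. Section 5.5 rules out ECG recording during echocardiography after randomisation. ECG monitoring during the exercise test is brief and for safety. None of these can measure AF burden over six months.

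**Step 3: can AF occur in these patients?** Yes. Section 4.1 excludes permanent or persistent AF, and paroxysmal AF only where there was a sustained episode (over 24 hours) in the six months before screening. It admits patients whose persistent AF has resolved.

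**Step 4: size.** The plan gives no figure for arrhythmia burden, so there is none to reproduce. Two quantities are needed, and the documents give neither:
- f: the share of control periods programmed VVI;
- s: the sensitivity of atrial arrhythmia detection in VVI.

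Assume equal true burden B in both states, the same mean burden in VVI and non-VVI control periods, and full detection outside VVI. Then:

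- recorded burden, active = B
- recorded burden, control = B × [(1 − f) + f·s] = B × [1 − f(1 − s)]
- apparent on/off ratio = 1 / [1 − f(1 − s)]

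| f | s | 1 − f(1 − s) | Apparent ratio (true ratio 1.0) |
|---|---|---|---|
| any | 1 | 1.000 | 1.00 |
| 0 | any | 1.000 | 1.00 |
| 10% | 0 | 0.900 | 1.11 |
| 25% | 0.5 | 0.875 | 1.14 |
| 25% | 0 | 0.750 | 1.33 |
| 50% | 0.5 | 0.750 | 1.33 |
| 50% | 0 | 0.500 | 2.00 |

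**Step 5: could such a gap be mistaken for an effect?** As an illustration, AF in a period was treated as yes/no and no true effect was assumed. The 126 evaluable patients of section 8.1 were compared by a two-sided exact McNemar test at 5% (20,000 simulated trials per scenario). The first false-significance figure assumes AF is independent between periods; the second assumes the same patients have it in both.

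| True AF per period (assumed) | f | s | Recorded, active v control | False significance |
|---|---|---|---|---|
| 10% | 25% | 0.5 | 10% v 8.8% | 3.6%; 0.6% |
| 20% | 25% | 0 | 20% v 15% | 14%; 61% |
| 20% | 50% | 0 | 20% v 10% | 53%; 99% |

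The plan's own model for burden may behave differently. The table shows only that the consequence runs from negligible to decisive, depending on inputs the documents do not supply.

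**The case against.** **The decisive step is outside the documents.** A mode code describes the sensing used for pacing and does not by itself say what the diagnostics store. Every patient has a right atrial lead, and sections 6.2 and 6.3 refer to manufacturer manuals that are not at hand. If these devices record atrial arrhythmia fully in VVI, the bias is zero. This stands. A reader might infer that the AF comparison is biased, or that His pacing will look pro-arrhythmic; the documents support neither as fact. They show only that equal recording is not secured.

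**The comparison itself is not spelled out.** Item (6) of section 2.4 speaks of measures being recorded, where items (2) to (4) speak of changes. It also contains fluoroscopy time, which arises once, before randomisation, and cannot enter a crossover model. Section 8.2(ii) assigns several item (6) measures to descriptive safety analysis. This stands in part: arrhythmia burden is not on that descriptive list, so the general sentence on secondary outcomes appears to reach it. Its definition may sit in the SAP, but a SAP cannot restore missing recordings.

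**Other routes detect AF.** Adverse events are recorded in both states with narrow exemptions (7.2), and arrhythmia admissions are anticipated (7.3). This limits the chance that clinically important AF in control goes unseen, but it does not measure burden.

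**The safety consequence is limited.** Any bias would exaggerate harm from His pacing and not hide it. Section 11.3 leaves the DMC's data and blinding to its charter, so a misleading on/off display is not shown. Both points stand.

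**Instructions may exist elsewhere.** The implant guidance (1.2) or the study manual (10.4) could already settle device configuration. That is possible, and would make the change a matter of cross-reference.

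**Conclusion.** The point holds as a conditional one. The protocol names an atrial arrhythmia endpoint, appears to take it from the device, requires atrial sensing in one state and allows a mode without it in the other, and nowhere requires equal recording. If VVI reduces atrial recording, His pacing would falsely appear to raise AF. The apparent ratio is 1.0 with full detection in VVI or no use of VVI, 1.14 to 1.33 when a quarter of control periods are in VVI with half or no detection, and 2.0 when half are in VVI with no detection.

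This rests on three things the documents do not settle: whether atrial diagnostics continue in VVI, how often VVI is used in control, and that the burden endpoint comes from the device (inferred from section 6.4 and the neighbouring device measures in item (6)). It is therefore an inexpensive safeguard for one component of one secondary outcome and not a proven error. The primary endpoint, the sample size of 126 evaluable and 160 randomised, and ventricular arrhythmia burden are not touched by this argument.

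**What to change.** 1. State in sections 1.2 and 2.4(6) that atrial arrhythmia recording must be active and identically configured in both treatment states. The sponsor should reconcile the control modes listed in 1.2 and 5.4 with this endpoint. No mode is recommended here.
2. Record the programmed mode and the atrial-recording status for each period, and give both to the DMC with the arrhythmia data.
3. Where recording differed between periods, report AF and flutter burden descriptively. Present the on/off comparison restricted to patients with atrial recording in both periods as a sensitivity analysis only. The mode is discretionary, and when control is the second period it may be chosen after first-period arrhythmia has been seen, so that subset may be selected on the outcome. The report should say so.

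The cost is a line on the programming checklist, one or two data fields, and a smaller denominator for this one endpoint wherever recording was not matched.

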1.3 Risk / Benefit Assessment

The risks associated with pacemaker implantation include:

- ~1% of developing pneumothorax
- ~1% of infection of pacemaker
- ~1% of lead displacement or device malfunction
- < 1% risk of pericardial effusion
- ~ 3% risk of haematoma
- ~2% risk of access vein clot

In order to minimise these risks, procedures will be carried out by highly experienced, high volume pacemaker implanters. All procedures will be carried out in centres which have the facilities and expertise available to manage complications should they occur.

Potential benefits of pacing in this population

- Improvement in heart failure symptoms
- Prevention of bradycardia (while this population do not have a pacing indication for bradycardia they are at increased risk of developing higher degrees of conduction

block or sinus bradycardia). The pacemaker will prevent bradycardia from occurring and symptoms occurring as a result of this.

• Patients with prolonged PR interval and heart failure are at higher risk of adverse outcomes including death. While this study is not powered to assess for a mortality benefit it is possible that the risk of death will be reduced with pacing therapy.

The Data Monitoring Committee will meet regularly and will review adverse event rates. If they are found to be higher than expected then appropriate action will be taken.

